3.1.2. Subgroup analysis

Subgroup analysis for the primary efficacy endpoint will be performed for the subgroups defined in Table 4. In general, if there are less than 5 patients per treatment group in a subgroup, the statistical analysis will not be conducted but summary statistics will be presented. However, for some patients, subgroups might be pooled to have sufficient patients per treatment group to conduct the analysis. The details of pooling subgroups will be documented prior to unblinding.

Subgroups	Categories	Order
Age group (years)	≥ 18 to <65	1
	≥65	2
Sex	Female	1
	Male	2
Race	American Indian or Alaska Native	1
	Asian	2
	Black or African American	3
25 August 2022 Confidential		Page 15 of 65

Table 4 Subgroups based on demographics and baseline characteristics

Subgroups	Categories	Order
	Native Hawaiian or Other Pacific Islander	4
	White	5
	Other	6
Ethnicity	Hispanic or Latino	1
	Not Hispanic or Latino	2
Region	North America	1
	Europe	2
SBS anatomical classification	Group 1 (jejunostomy) ^a	1
	Group 2 (jejuno-colonic anastomosis)	2
	Group 3 (jejuno-ileo-colonic anastomosis)	3
	Other	4

Abbreviations: SBS: Short Bowel Syndrome

Notes: a: patients who do not have a colon-in-continuity as recorded in the CRF

Patients with their sex recorded as Unknown/Undifferentiated will be excluded from the sex subgroup analysis.

The analysis will be performed for patients in the FAS and conducted in a similar manner as for the primary analysis of the primary endpoint but including visit-by-treatment-by-subgroup interaction in the MMRM model. The treatment effect of OW and TW relative to placebo, will be estimated within the model, at Week 24 for each subgroup and presented with 95% CIs. No formal hypothesis testing will be performed.

If there are less than 5 patients per treatment group in a subgroup, the statistical analysis will not be conducted but summary statistics will be presented.

3.1.3. Impact of COVID-19

No sensitivity analyses are planned to assess the impact of COVID-19 on any of the confirmatory efficacy endpoints since actual PS volume is collected in a daily electronic diary which is not dependent upon attending clinical visits per the protocol Schedule of Assessments. Refer to Risk Assessment and Conclusion document dated 30-Nov-2020 entitled "Covid-19 pandemic contingency plan for glepaglutide phase 3 trials; ZP1848-17111 (EASE SBS 1) and ZP1848-17127 (EASE SBS 2).

3.1.4. Supportive analysis of primary endpoint derivation

The primary endpoint, actual weekly PS volume, will be derived as specified in Appendix A. The robustness of the primary analysis, with regard to the algorithm, will be explored through several supportive analyses, which each will address the impact of key algorithm elements. The analyses are considered 'supportive' as patients with missing PS entries continue in the trial, and no relevant intercurrent events are expected to trigger the missing entries.

Supportive estimator 1 is applying the derivation method specified in previous SAP versions (3.0 and 4.0) without any values carried forward. This is considered an extremely conservative estimate of the endpoint, as days without PS entries in the eDiary within a certain week will be imputed with the total weekly PS volume divided by the number of days of non-missing data.

Supportive estimator 2 and 3 assess the impact to the primary analysis by varying individual algorithm elements. That is by removing information collected through note-to-files, and increasing the minimum threshold necessary for calculating an endpoint with respect to percentage actual PS volume versus prescribed, respectively.

Supportive estimator 4 considers a continuum between main and supportive estimator 1, but without a threshold for setting the endpoint to missing. This is to explore the incremental impact of imputing missing PS entry days with either 0 L or the total weekly PS volume divided by the number of days of non-missing data.

To get an overview of the supportive estimators for the primary endpoint derivation, and each individual algorithm elements, please see Table 5.

Statistical Analysis Plan v6.0

Table 5 Overview of supportive analysis of primary endpoint derivation

	Main estimator	Supportive estimator 1	Supportive estimator 2	Supportive estimator 3	Supportive estimator 4
Algorithm element	Appendix A algorithm	SAP v3.0/4.0 algorithm	Appendix A algorithm w/o NTFs	Appendix A algorithm with less deviation from prescribed amount allowed	Tipping individual PS entry days
Threshold for setting endpoint missing	Yes, if actual PS entry days <7 and PS accounted for <90% vs prescribed PS	Yes, if actual PS entry days <4	Yes, if actual PS entry days <7 and PS accounted for <90% vs prescribed PS	Yes, if actual PS entry days <7 and PS accounted for <95% vs prescribed PS	No
If endpoint not set to missing and no. of PS entry days \neq 7, missing PS entry days will be imputed with	0	Average of non-missing days	0	0	Tipping (from 0 to 1 by 0.1)*Average of non- missing days
Flexible window for endpoint assessment	7 consecutive days within the period between 1 and 14 days preceding visit date (30 days for baseline)	7 consecutive days preceding visit date	7 consecutive days within the period between 1 and 14 days preceding visit date (30 days for baseline)	7 consecutive days within the period between 1 and 14 days preceding visit date (30 days for baseline)	7 consecutive days preceding visit date
Allow window for endpoint assessment to cross previous visit	No (with exemption of Week 1 and 2)	Yes	No (with exemption of Week 1 and 2)	No (with exemption of Week 1 and 2)	Yes
Information from NTFs used	Yes	No	No	Yes	No

Abbreviations: PS: parenteral support, NTF = note-to-file

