7.2 Inclusion Criteria

The patient must meet all of the following inclusion criteria:

1. Informed consent obtained before any trial-related activity.
2. Age ≥ 18 years and ≤ 90 years at Screening.
3. Diagnosis of SBS defined as remaining small bowel in continuity of estimated less than 200 cm [equal to 79 inches] and with the latest intestinal resection being at least 6 months prior to Screening and considered stable with regard to PS need. No restorative surgery planned in the trial period.
4. Requiring PS at least 3 days per week.
5. Willing to adhere to an individual pre-defined drinking menu during 48-hours measuring intervals.
6. Willing to maintain a stable weight ($\pm 5\%$) for the duration of the trial (24 weeks).
7. Having:
 - a. A stoma Or
 - b. Colon-in-Continuity (CiC) with documented colonoscopy performed during Screening and which does not give rise to any safety concerns.
1. Note: A colonoscopy performed within 6 months prior to Screening and not giving rise to any safety concerns is accepted. For patients with a remnant colon, which is not connected to the passage of foods and is thereby dormant, a computerized

tomography (CT) scan or magnetic resonance imaging (MRI) (if standard of care at site) will suffice at the discretion of the investigator.

8. Having a) a stoma Or b) colon-in-continuity (CiC) and able to separate stool and urine during the 48 hours measuring intervals.

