8.4 Treatment Compliance

Treatment compliance is encouraged by patients receiving reminders from their eDiary for trial drug administrations. Patients are requested to enter details regarding trial drug administration (including date and time of the day as well as DUN) and injection site area used (i.e., abdomen, thigh) in the eDiary. Patients are to record PS use (including bag name, volume, infusion date, and duration) in the eDiary on an ongoing basis.

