If the loop is not stopped in steps 1, 2, 3 and 4 then a new 7-day period is defined from the visit date minus 2 days to visit date minus 8 days and the loop is re-started (steps 2, 3, and 4). For post-baseline visits, the loop can be re-started until the new 7-day period is from the visit date minus 8 days to the visit date minus 14 days. For baseline visits, the loop can be re-started until the new 7-day period is from the visit date minus 14 days. For baseline visits, the loop can be re-started until the new 7-day period is from the visit date minus 24 days to the visit date minus 30 days. If the loop reaches earliest allowed period without stopping then AVAL will be set to missing, ANLxxFL =' ' and ANLxxREA = "No valid period identified".

Note that, if there are 7 days without relevant prescribed PS prior to a visit, then the period will be considered valid, AVAL will be derived as the sum of available volumes found in the 7-day prior to the visit, and the ANLxxFL will be set to 'Y'. If and there are no PS volume entries in the eDiary, AVAL will be set to 0 (zero).

Note: that for calculating \geq 90% volume accounted for, the relevant prescribed volume will be calculated using the same time-period as the actual volume, in contrast to the prescribed parameter described above, which strictly uses the values in the period visit date minus 1 day to visit date minus 7 days for the derivation.

Prescribed and actual weekly PS volume based on a 14-day period

The same rules as stipulated above apply when calculating the **actual** weekly PS volume based on a 14-day valid period, except that the loop can be re-started until the 14-day period is from the visit date minus 28 days to the visit date minus 15 days.

Note that, if the last prescription end date is more than 14 days prior to the visit, and there are no PS volume entries in the eDiary, the actual weekly PS volumes (AVAL) will be set to 0, and ANLxxFL will be set to 'Y'.

Note that, for the actual volumes the Day 3, Week 1 and Week 2 visits will not be included in the dataset, and hence the Week 4 valid 14-day period is allowed to start before the date of any of these visits.

The **prescribed** weekly PS volume will be derived as described above but based on the period from the visit date minus 1 to the visit date minus 14. Note that, if the last prescription end date is more than 14 days prior to the visit, the prescribed weekly PS volumes (AVAL) will be set to 0, and ANLxxFL will be set to 'Y'.

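### Supportive estimator 1 (SAP 3.1.4, Table 5) fills planned PS-free days as if they were missing diary days, so unless those days carry a 0 L entry it does not measure weekly PS volume; estimator 4 shares the fault in part

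*SAP*

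**What the plan says.** SAP 3.1.4 sets out supportive analyses meant to show whether the primary result is robust to the algorithm that turns diary records into an actual weekly PS volume.

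- **Estimator 1** applies the derivation of SAP versions 3.0 and 4.0: "days without PS entries in the eDiary within a certain week will be imputed with the total weekly PS volume divided by" a count of days with data. Table 5 sets the endpoint to missing on this condition: "Yes, if actual PS entry days <4". The SAP comments: "This is considered an extremely conservative estimate of the endpoint".
- **Estimator 4** spans the range between the main estimator and estimator 1, "but without a threshold for setting the endpoint to missing". Table 5 gives its fill as "Tipping (from 0 to 1 by 0.1)*Average of non- missing days".
- **The main estimator** (Appendix A) fills empty days with 0. It accepts a week with fewer than 7 entry days if at least 90% of the prescribed volume is accounted for. It sets the weekly volume to 0 when no PS was prescribed and nothing was entered.

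On diary content, Protocol 8.4 says: "Patients are to record PS use (including bag name, volume, infusion date, and duration) in the eDiary on an ongoing basis". On the population, Protocol 7.2 requires: "Requiring PS at least 3 days per week". Protocol Table 4 provides for regimens of 0 to 7 PS days per week, and a reduction of at least one PS day per week is the second key secondary endpoint.

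**The concern.** A day without a diary entry can mean two things: the patient forgot to record an infusion, or no infusion was planned. Estimators 1 and 4 do not separate them, and neither refers to the prescription. Planned PS-free days are routine in this trial, and adding them is one of the ways the drug is expected to help.

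If such days are blank in the diary, these analyses change the endpoint even when the diary is perfect. A gap between estimator 1 and the primary result could then be read as dependence on missing entries when it only reflects days off PS. Agreement between them could equally be accidental.

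**Working it through.** The SAP gives no figure for this rule, so there is none to reproduce. The rule can be applied directly.

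**Premise.** The calculation assumes that a planned PS-free day has no entry. Three provisions point that way:
- Protocol 8.4 describes an infusion record (bag, volume, date, duration) and mentions no zero record.
- The main estimator has a route for weeks with fewer than 7 entry days, tied to the prescribed volume and with zero fill. That suits patients with planned days off.
- SAP 5.3 and Appendix A need a special rule giving 0 L when PS has stopped and no entries exist.

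**Formulas.** Let d be the number of entry days in the 7-day window, v the mean volume per entry day, and f the tipping factor.
- True weekly volume with a complete diary: d x v.
- Estimator 1: d x v + (7 - d) x v = 7v if d is at least 4, otherwise missing. The number of PS days drops out.
- Estimator 4: d x v + f x (7 - d) x v, with no missing threshold. With d = 0 the average is 0/0.

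**Results.** Diary complete; volumes per infusion are illustrative assumptions; entries are changes in L/week.

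| Baseline to Week 24 | True | Estimator 1 | Est. 4, f = 0 | f = 0.5 | f = 1 |
|---|---|---|---|---|---|
| 7 x 2.0 to 5 x 2.0 | -4.0 | 14 - 14 = 0 | -4.0 | -2.0 | 0 |
| 6 x 2.0 to 4 x 1.5 | -6.0 | 10.5 - 14 = -3.5 | -6.0 | -4.75 | -3.5 |
| 4 x 2.0 to 4 x 1.5 | -2.0 | 10.5 - 14 = -3.5 | -2.0 | -2.75 | -3.5 |
| 7 x 2.0 to 3 x 2.0 | -8.0 | Week 24 missing | -8.0 | -4.0 | 0 |
| 3 x 2.0 to 2 x 2.0 | -2.0 | both missing | -2.0 | -1.0 | 0 |
| 4 x 2.0 to none | -8.0 | Week 24 missing | no average | no average | no average |

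The first two rows show that the part of a reduction achieved by dropping days is lost. The third shows the opposite error: with d unchanged, a cut in volume per infusion is multiplied by 7/d, here 7/4 x (-2.0) = -3.5. For scale, the treatment differences assumed in SAP 2.6 are 4.5 - 2.3 = 2.2 and 4.3 - 2.3 = 2.0 L/week.

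**What happens to the missing values,** assuming the primary imputation is used:
- A missing baseline is imputed from a model using FAS patients, not only placebo (note to SAP Table 3).
- Intermittent gaps are imputed within arm under MAR. Monotone gaps use the placebo model, conditional on the patient's earlier values (SAP 5.3.1).
- So a patient brought to 0-3 PS days and staying there to Week 24 would be imputed from the placebo model.

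**If the premise fails.** With a 0 L entry on each day off, all 7 days count as entry days. The 5 x 2.0 L week then reads 10 L, the change is -4 L/week, and the distortion disappears.

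**The case against.** The strongest objection is that the premise is unproven. SAP 2.5 says PS volume is recorded daily, and SAP 3.1.3 refers to a daily electronic diary. Step 3 in Appendix A accepts a week in which every day has a volume accounted for. Without zero entries, that step would ordinarily serve only patients on PS 7 days a week. The 4-day threshold also sits oddly with entry at 3 PS days, unless zero days counted as entries. This doubt stands, and the point is conditional on it. It does not remove the need for a definition, because comparing gaps with the prescription does no harm under either reading.

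Several stronger readings are tempting, and the documents do not support them:
- A reader might infer that estimators 1 and 4 alike erase reductions and turn the best responders into missing values. Table 5 gives estimator 4 no missing threshold. It is exact at factor 0 and loses the whole dropped-day part only at factor 1.
- A reader might infer that the effect can only shrink. The 4 x 2.0 L to 4 x 1.5 L case shows it can be inflated, so the net direction is unknown.
- A reader might infer that every value set to missing is replaced from placebo. That holds only for monotone gaps.

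Two further objections have weight. The analyses are supportive only. And the SAP 3.0/4.0 text is not available here, so any special rule it had for PS-free or weaned weeks cannot be checked.

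**Conclusion.** The point holds, on condition that planned PS-free days carry no 0 L entry. Estimator 1 then measures 7 times the mean volume per infusion day, with errors per patient of the order of the assumed treatment difference or larger (4 L/week for a 7-to-5-day reduction at 2 L), and in either direction. Its threshold also sets to missing patients on 3 PS days at baseline and patients reduced to 0-3 days, including those weaned off. Estimator 4 is affected by degree and has no defined value for a patient with no entries.

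A reader might infer that the primary result itself is in doubt. It is not: the Appendix A derivation and the confirmatory tests do not use these rules. What is weakened is the ability of estimators 1 and 4 to show robustness to diary gaps. The net effect on the estimated treatment difference cannot be calculated from the documents, because it depends on how patients split their reductions between fewer days and smaller infusions.

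**What to change.** In SAP 3.1.4 and Table 5:

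1. State whether a PS-free day carries a 0 L entry, and count as missing only entry days that leave the week short of the relevant prescribed volume.
2. Where a day-level schedule is usable, fill only scheduled PS days that have no entry. Otherwise cap the filled weekly total at the relevant prescribed volume already computed in Appendix A, but never below the recorded volume.
3. Express the estimator 1 threshold relative to prescribed PS days or volume instead of 4 of 7 calendar days.
4. Carry over the Appendix A rule giving 0 when no PS is prescribed and there are no entries.

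For a complete diary that follows the prescription, both estimators then return d x v: 7 to 5 days at 2 L reads -4, and 4 x 2.0 L to 4 x 1.5 L reads -2.0. The test still responds to a real gap. With 5 x 2 L prescribed and 4 days entered, the capped estimator 1 total is min(8 + 3 x 2, 10) = 10 L, against 8 L recorded.

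**Cost.** SAP wording and some programming. The visit procedures in the protocol record a weekly schedule, but Appendix A describes prescriptions in L/week per bag with dates and no clear day-level field, so the cap may be the practical route. Under the cap, estimator 4 can reach its ceiling before factor 1 (in the example, 8 + 6f = 10 at f = 1/3). Estimator 1 would no longer exactly reproduce the SAP 3.0/4.0 algorithm. If that version is also kept, it should be labelled as biased in either direction and not as extremely conservative.

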3.2. KEY SECONDARY EFFICACY ENDPOINTS

The following 4 key secondary efficacy endpoints will be analyzed to assess the treatment effect using the FAS. The key secondary endpoints will be derived based on the actual weekly PS volume or the number of days on actual PS a week, using the selected valid 7-day period at Week 12, 20, and 24, respectively. For details on the derivation see Appendix A.

First key secondary efficacy endpoint: Clinical response, defined as at least 20% reduction in actual weekly PS volume from baseline to both Weeks 20 and 24

The primary estimand will handle the intercurrent event of treatment discontinuation under a 'composite strategy', i.e. incorporating the intercurrent event in the response definition. For patients who discontinue treatment prematurely, a non-response will be imputed, indicating failure to randomized treatment. This assesses the treatment effect of

• Difference in percentage of clinical response without treatment discontinuation between glepaglutide treatment group and placebo in the SBS population.

Missing data for other reasons will be imputed with a non-response.

The difference in clinical response rates between each glepaglutide group and the placebo will be calculated using Mantel-Haenszel weighing and presented with 95% confidence intervals (using the Wald estimation method). Whether the difference equals zero will be tested using the Cochran-Mantel-Haenszel (CMH) adjusted for the stratification factor. In the presence of strata with zero counts in the crosstabulation between stratification factor and treatment, an unadjusted difference in clinical response rates between each glepaglutide group and the placebo will be calculated (i.e. without stratification), to avoid inappropriate weighing of the risk differences in each stratum. The null hypothesis of a difference equals zero will still be tested using the Cochran-Mantel-Haenszel (CMH), with a single contingency table.

As a sensitivity analysis of the primary estimand of first key secondary efficacy endpoint, the actual weekly PS volume will be derived using a valid 14-day period prior to the visit. For details on the derivation of actual weekly PS volume within a 14-day period, see Appendix A. Handling of missing data and analysis of this endpoint will follow that of the primary estimand of first key secondary efficacy endpoint.

In addition, a supplementary estimand will be included using a 'treatment policy strategy' assessing the treatment effect of

• Difference in percentage of clinical response between glepaglutide treatment group and placebo in the SBS population, regardless of whether treatment is discontinued.

Response status will be derived from the CR-imputed data sets generated from the multiple imputation approach described for the primary estimand (main estimator) of the primary efficacy endpoint. The difference will be analysed in the same way as the primary analysis of first key secondary efficacy endpoint. The test statistics based on the MI will be combined by applying Rubin's rule after Wilson-Hilferty transformation (Wilson et al 1931).

25 August 2022

To get an overview of the different estimands and estimators for the binary key secondary efficacy endpoints, and how missing data will be handled, please see Table 6.

Second key secondary efficacy endpoint: Reduction in days on $PS \ge 1$ day/week from baseline to Week 24

The same estimands (main estimators) and sensitivity estimator will be investigated, as for the first key secondary efficacy endpoint (see Table 6). The same analysis method will be applied as well.

Primary 'composite' estimand for the second key secondary efficacy endpoint

• Difference in percentage of reduction in days on $PS \ge 1$ day/week from baseline to Week 24 without treatment discontinuation between glepaglutide treatment group and placebo in the SBS population.

Supplementary 'treatment policy' estimand for the second key secondary efficacy endpoint

• Difference in percentage of reduction in days on $PS \ge 1$ day/week from baseline to Week 24 between glepaglutide treatment group and placebo in the SBS population, regardless of whether treatment is discontinued.

For the supplementary estimand, response status is derived using the same MI model as for primary analysis of primary efficacy endpoint with the number of PS days as dependent variable.

Third key secondary efficacy endpoint: Change in actual weekly PS volume from baseline to Week 12

The same estimands (main estimators) and sensitivity estimators will be investigated, as for the primary efficacy endpoint (see Table 3). The same analysis method will be applied as well (see 3.1).

Primary 'treatment policy' estimand for the third key secondary efficacy endpoint

• Difference between mean change from baseline in actual weekly PS volume at 12 weeks in the SBS population regardless of whether treatment is discontinued.

Supplementary 'hypothetical' estimand for the third key secondary efficacy endpoint

• Difference between mean change from baseline in actual weekly PS volume at 12 weeks in the SBS population, as if treatment discontinuation never occurred.

Fourth key secondary efficacy endpoint: Reduction in weekly PS volume of 100% (weaned off) at Week 24

The same estimands (main estimators) and sensitivity estimator will be investigated, as for the first key secondary efficacy endpoint (see Table 6). The same analysis method will be applied as well.

Primary 'composite' estimand for the fourth key secondary efficacy endpoint

25 August 2022

• Difference in percentage of reduction in weekly PS volume of 100% (weaned off) at Week 24 without treatment discontinuation between glepaglutide treatment group and placebo in the SBS population.

Supplementary 'treatment policy' estimand for the fourth key secondary efficacy endpoint

• Difference in percentage of reduction in weekly PS volume of 100% (weaned off) at Week 24 between glepaglutide treatment group and placebo in the SBS population, regardless of whether treatment is discontinued.

Note, the main analyses of the primary estimands follow the treatment policy strategy for the primary and third key secondary endpoints and the composite strategy for the first, second and forth key secondary endpoint. This is according to the confirmatory testing strategy described in the protocol version 10.0.

Table 6 Overview of estimands and handling of missing data for binary key secondary efficacy endpoints

Intercurrent event	Data observed or missing	Primary estimand 'Composite'		Supplementary estimand 'Treatment policy'
		Main estimator	Sensitivity estimator – PS vol derived based on 14-day period	Main estimator
Prematurely discontinuation of IMP	Observed	Non-response	Non-response	Value used as observed
	Missing	Non-response	Non-response	Response status derived from MI (CR Placebo)*
No prematurely discontinuation of IMP	Observed	Value used as observed	Value used as observed	Value used as observed
	Missing	Non-response	Non-response	Response status derived from MI (CR Placebo)*

Abbreviations: MI = multiple imputation, CR = copy reference

*For 'Reduction in weekly PS volume of xx%' endpoints, response status is derived from the values generated by the MI model used for primary analysis of primary efficacy endpoint. For 'Reduction in days on $PS \ge 1$ day/week from baseline to Week 24' endpoint, response status is derived using the same MI model as for primary analysis of primary efficacy endpoint with the number of PS days as dependent variable.

[figure not shown]
